5 GENERAL STATISTICAL METHODS

5.1 Sample Size Justification

Assuming a mean ABR of 18 with standard deviation (SD) = 14 in the on-demand arm (patients randomized to receive on-demand bypassing agents) and a mean ABR of no more than 4 with SD = 6 in the fitusiran treatment arm (patients randomized to receive fitusiran) in either the efficacy period or treatment period, with a sample size of 14 evaluable patients in on-demand arm and approximately 28 evaluable patients in the fitusiran treatment arm, it is projected that the study will have greater than 90% power for testing treatment difference in mean ABRs. This power estimation was based on negative binomial regression model with a 2-sided type I error rate of 0.05.

The planned sample size is 54 randomized patients assuming a 20% drop-out rate.

In the China Addendum #1 to protocol amendment 2, it specifies that before any Chinese patients are randomized to receive 80 mg of fitusiran subcutaneous (SC) treatment, three (3) subjects in China will be enrolled into a China specific non-randomized fitusiran treatment arm to receive fitusiran as a SC injection administered every 4 weeks, with initial starting dose of 50 mg SC. After the observation period for these 3 patients is completed and dose escalation is authorized by the Sponsor, the 3 patients will undergo dose escalation to receive 80 mg of fitusiran as a SC injection every 4 weeks. These 3 patients will not be included in the ITT Set for the efficacy analyses but will be included in the Safety Set for the safety analyses. Their efficacy data will be included in separate listings.

5.2 General Methods

All data listings that contain an evaluation date will contain a study day relative to the day of Day 1 visit when baseline assessments are performed and fitusiran first dose is given, which is designated as Day 1. The Day 1 visit date should coincide with randomization date but could occur within 3 days after the randomization. If the fitusiran first dose is given after Day 1 visit, a study day will be calculated relative to the day of first dose. Study days will be calculated as evaluation date – Day 1 visit date (or first dose date) +1 and pre-Day 1 visit days will be calculated as evaluation date – Day 1 visit date (or first dose date). For example, the day prior to Day 1 visit will be Day –1 and the day after Day 1 visit will be Day 2, etc. There will be no Study Day 0.

Categorical variables will be summarized using counts and percentages. Continuous variables will be summarized using the number of patients (n), mean, SD, median, interquartile range (Q1, Q3), minimum value (min), and maximum value (max). The precision of the measurement for each continuous variable will be used to determine the number of decimal places to present in tables, figures and derived listings. Minimum and maximum values will be reported with the same precision as the units of measure. The other statistics will be reported to 1 greater decimal place. Any values that require transformation to standard units (metric or SI) will be converted with the appropriate corresponding precision.

5.3 Computing Environment

All statistical analyses will be performed using SAS statistical software Version 9.4 (or later), unless otherwise noted.

5.4 Timing of Analyses

The primary efficacy and safety analyses will be performed after all patients have either completed the 9-month treatment period or withdrawn from the study.

No interim analysis is planned for this study.

5.5 Baseline Definitions

Unless noted otherwise, baseline for on demand group is defined as the last non-missing value on or before Day 1 visit. Baseline for fitusiran group is defined as the last non-missing value before 1st dose of fitusiran or the last non-missing value on or before randomization date for patients who were randomized but never exposed to fitusiran.

ECG measurements are taken in triplicate. For the on demand group, the average of the first triplicate readings on or before Day 1 visit or on screening visit will be used as baseline. For fitusiran group, the average of the last triplicate readings before 1st dose is used as baseline.

For questionnaire assessments, the last non-missing value on or before Day 1 visit will be used as baseline. For fitusiran patients, the last non-missing value on or before date of 1st dose of fitusiran or the last non-missing value on or before randomization date for patients who were randomized but never exposed to fitusiran will be used as baseline.

5.6 Randomization Stratification Factors

Randomization for this study is stratified by the number of bleeding episodes in the 6 months prior to study entry (≤ 10 vs >10).

5.7 Multiple Comparisons/Multiplicity

To control for the familywise error rate at 0.05 level in the testing of primary and selected secondary endpoints, a hierarchical testing approach will be used. The endpoints will be tested in the following order:

Global protocol	US protocol	2-Sided alpha
1. ABR in the efficacy period	1. ABR in the treatment period	0.05
2. ABR in the treatment period	2. ABR in the efficacy period	0.05
3. Annualized spontaneous bleeding rate in the efficacy period		0.05
4. Annualized joint bleeding rate in the efficacy period		0.05
5. Change in Haem-A-QOL physical health score and total score in the treatment period		0.05

If testing of any of the endpoints is not statistically significant, formal testing of subsequent endpoints will stop and the null hypothesis for subsequent tests will not be rejected. For endpoint 5, change in Haem-A-QOL physical health score in the treatment period will be tested first followed by change in Haem-A-QOL total score in the treatment period. The testing of the secondary endpoint ABR in the onset period will not be included in this hierarchical testing procedure.

5.8 Missing Data

On the eDiary device, it is not possible to leave questions unanswered or to enter partial data.

In the bleeding diary pages of the CRF, it is possible to have missing time of a treatment or a bleed. In that case, it is assumed that the bleeds and treatments with missing time occurred at 12:00 am.

Additional details will be included in the sections describing the analyses corresponding to each endpoint.

5.9 Protocol Deviations

A protocol deviation is any change, divergence, or departure from the study design or procedures defined in the clinical protocol. Protocol deviations will be classified by medical review prior to primary analysis and critical and major protocol deviations will be identified. A critical protocol deviation is a deviation that adversely affects data integrity, patient's right and safety. A major protocol deviation is a deviation that potentially can affect data integrity, patient's right and safety. All critical and major deviations related to trial inclusion or exclusion criteria, conduct of the trial, patient management or patient assessment will be described in the clinical study report.

The Sponsor or designee is responsible for producing the final protocol deviation file. This file will include a description of each protocol deviation and whether or not this deviation is classified as a critical or major protocol deviation. This file will be finalized prior to performing the primary analysis.

5.10 Derived Analysis Visit Windows

A scheduled measurement will be used if it is available. Otherwise, derived analysis visit window will apply to data collected on unscheduled visits and early withdrawal visits (such as PD, clinical laboratory parameter, vital signs, etc.) to re-allocate a post-baseline unscheduled measurement to a scheduled measurement, except for PK and ECG, using Study Day (defined in [Section 5.2](#)), according to the following allocation table:

Analysis visit label	Target study day	Derived Window in study days	
		lower bound	upper bound
Baseline	1	-INF	1
Day 15	15	2	21
Day 29	29	22	35
Day 43	43	36	49
Day 57	57	50	70
Day 85	85	71	98
Day 113	113	99	126
Day 141	141	127	154
Day 169	169	155	182
Day 197	197	183	210
Day 225	225	211	238
Day 253	253	≥ 239	EOS/ET visit date if EOS/ET visit is ≥ 239
Day 281	28 days after EOS/ET for patients who complete the AT F/U visits	1 day after EOS/ET visit	999
Endpoint	Last non-missing post-baseline assessment on or before EOS/ET visit		

If more than one data point is within a window the visit closest to the target study day will be selected. If there are multiple visits with the same distance from the scheduled visit day, the last value will be selected.

5.11 Geographic Region

Geographic region will consist of the following categories: North America, Europe, Asia, Other. The countries in each region are the following:

- North America (United States, Canada)
- Europe (Bulgaria, Denmark, France, Germany, Hungary, Italy, Portugal, Spain, Turkey, Ukraine, United Kingdom)
- Asia (China, India, Japan, Korea, Malaysia, Taiwan)
- Other (Australia, South Africa)

6 STATISTICAL ANALYSES

6.1 Patient Disposition

Patient disposition will be tabulated for the following categories:

- patients screened
- patients screen failed
- patients randomized
- patients in each analysis population
- patients treated (fitusiran arm only)
- patients who completed the study treatment (9-month treatment period, fitusiran arm only)
- patients who discontinued study drug and primary reasons for study drug discontinuation (fitusiran arm only)
- patients who discontinued study drug and primary reasons for study drug discontinuation due to Covid-19 (fitusiran arm only)
- patients who completed the study
- patients who withdrew prior to completing the study but completed Month 9 visit
- patients who withdrew prior to completing the study and primary reasons for withdrawal.
- Patients who withdrew prior to completing the study and primary reasons for withdrawal due to Covid-19

Patient disposition will be presented by randomized treatment arm and overall, as applicable.

Patients randomized by country, site and randomization stratification factor stratum will be summarized by randomized treatment arm and overall.

6.2 Demographics and Baseline Characteristics

Demographic and baseline characteristics, baseline disease characteristics, and medical history information will be summarized by treatment arm and overall for the ITT Analysis Set, Safety Analysis Set (if different from the ITT Analysis Set), and the Per-protocol Analysis Set. No formal statistical comparisons will be performed.

Age, height, weight, and body mass index (BMI) will be summarized using descriptive statistics. Age group, sex, race, ethnicity, and region will be summarized by presenting the numbers and percentages of patients in each category.

The following baseline disease characteristics will be summarized: age at diagnosis, time from diagnosis to randomization, hemophilia type, and number of bleeding episodes in the last 6 months prior to the study.

6.3 Efficacy Analysis

Bleeding Episode Definitions

The primary source of bleeding data will be the eDiary. Additional bleeding data may be captured from the bleeding diary pages of the CRF, if not reported in the eDiary. Any other sources of bleeding data will be discussed in the CSR.

A bleeding episode is defined as any occurrence of hemorrhage that may require administration of BPA or factor. Bleeding episodes sustained during sports and recreation will be counted as traumatic bleeding episodes.

Bleeding or any symptoms of bleeding at the same location that occur within 72 hours of the last injection used to treat a bleed or 72 hours after an untreated bleed at that location will be considered a part of the original bleeding event, and will count as one bleeding episode. Any bleeding symptoms that begin more than 72 hours from the last injection used to treat a bleed or 72 hours after an untreated bleed at that location will constitute a new bleeding event.

Traumatic bleeds that occur in different locations simultaneously (same date/time) in the same patient will be considered as one bleeding episode. Spontaneous bleeds that occur simultaneously (same date/time) in different locations in the same patient will be considered as separate bleeds.

Efficacy analysis will focus on observed data as collected, unless otherwise specified. Patients who discontinue study drug during the study will be strongly encouraged to continue study participation including the recording of bleeding episode data. Only bleeding episodes that are treated with BPA/factor will be included in the primary analysis of endpoints evaluating bleeding.

Efficacy Period and Treatment Period

In the protocol, for the purpose of ABR calculation, fitusiran “Onset Period”, “Efficacy Period” and “Treatment Period” are defined. The Onset Period is defined as the first 28 days after the first dose of fitusiran, during which the AT lowering capacity of fitusiran is increasing but has not yet reached therapeutic levels. The Efficacy Period is defined as starting on Day 29 when the AT lowering capacity of fitusiran has achieved therapeutic target range. The Treatment Period is defined as the onset period plus the efficacy period. The window for each period is modified and summarized in the table below. The corresponding window is applied to on-demand arm for analysis purpose.

Fitusiran arm/On-demand arm	
Onset Period	Day 1 to the earlier of Day 28 and the last day of bleeding follow up
Efficacy Period	Day 29 to the earliest of (Day 246, or the last day of bleeding follow up)
Treatment Period	Onset period plus the efficacy period

The last day of bleeding follow up is defined as the deactivation date captured in eDiary.

If a patient does not have bleeding episode data collected after Day 28 due to early study discontinuation, the efficacy period will be from Day 1 to the earlier of date of study discontinuation and the last day of bleeding follow up.

The onset period, efficacy period and treatment period also exclude the period of following intercurrent events to avoid confounding of treatment effect for the primary efficacy analysis based on On-Treatment Strategy.

- After one month (28 days) from fitusiran treatment discontinuation in the fitusiran efficacy period. Excluding bleeding data after one month from fitusiran treatment discontinuation is considered reasonable and adequate considering that fitusiran is dosed monthly and EOS is one month after last dose of fitusiran
- Perioperative period of major surgery. The perioperative period is defined as the day of the surgery through the final day on which supplemental hemostatic or antithrombotic treatments are administered as part of the perioperative treatment plan.
- Period of minor surgery is defined as the Perioperative period of surgery above or to 72 hours from the end of surgery, whichever is later.
- Period of Antithrombin treatment is defined as the first day of antithrombin treatment through the final day on which antithrombin or other anticoagulant therapies are administered plus 5 half-lives of that specific product.
- After prophylactic treatment with emicizumab, BPA or factor.

The summary statistics for number of patients who are lost-to-follow-up and who had each intercurrent event will be provided.

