### *Fitusiran Treatment During the Perioperative Evaluation Period*

For reference, see Appendix (Section 11.2.1) for definitions of minor and major surgery.

If the need for a major surgery arises during the trial and the procedure is not an emergency or urgent, it is recommended that the procedure be postponed until after completion of the trial.

For minor operative procedures, dosing with fitusiran may continue uninterrupted.

If the need for emergency or urgent major surgery arises during the trial, the patient should be managed medically according to the guidelines above. If a fitusiran dose is scheduled to occur on or in close proximity to the day of surgery, or anytime during the perioperative period, the dose should be withheld. The Perioperative Evaluation Period is defined as the day of the surgery through the final day on which supplemental hemostatic or antithrombotic treatments are administered as part of the perioperative treatment plan. Fitusiran dosing may be resumed at the next scheduled visit following the Perioperative Evaluation Period at the discretion of the Investigator. If multiple consecutive doses of fitusiran are withheld, the Investigator will consult with the study Medical Monitor, who will determine if the patient may continue on study.

Perioperative assessments will be performed in patients undergoing surgery during the study as described in Appendix Section 11.2.2 and as scheduled in Table 10.

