##### 8.2.5.1. Primary Endpoint

The primary analysis will be performed on the ITT Analysis Set and will include all bleeding episodes occurring in the efficacy period (Day 29 to Day 246) including bleeding episode data collected after discontinuation of IMP. If a patient does not have bleeding episode data collected after Day 28 (eg, due to early study discontinuation), the available bleeding episode data starting from Day 1 will be used as bleeding episode data of the fitusiran period in the primary analysis. To avoid confounding the treatment effect, bleeding episode data during and after major surgery, AT administration, major trauma, or initiation of prophylaxis treatment with BPAs will be excluded from the primary analysis.

The number of bleeding episodes will be analyzed using a negative binomial model with fixed effects of treatment arm and the number of bleeding episodes in the 6 months prior to study entry ( $\leq 10$  vs  $> 10$ ). The logarithm number of days that each patient spends in the efficacy period matching the bleeding episode data being analyzed will be included as an offset variable to account for unequal follow-up time due to early withdrawal or surgery. The p-value comparing bleeding rates in the 2 treatment arms and the ratio of bleeding rates in the fitusiran treatment arm to the on-demand arm along with its 95% CI will be presented. The estimated mean ABRs in 2 treatment arms along with their 95% CIs will be presented from this model. In addition, summary statistics for ABR, including the median and interquartile range, will be presented for each treatment arm, where ABR is defined as:

$$\frac{\text{total number of qualifying bleeding episodes}}{\text{total number of days in the respective period}} \times 365.25$$

---

Patients who discontinue treatment during the study will be encouraged to continue recording bleeding episode data.

Sensitivity analyses will be performed to evaluate the impact of missing data under different missing data mechanisms and details will be specified in the statistical analysis plan.

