## 11.2. Perioperative Schedule of Assessments

### 11.2.1. Definitions of Minor and Major Surgery

Minor surgery is defined as any invasive operative procedure in which only skin, mucous membranes, or superficial connective tissue is manipulated and does not meet the criteria for major surgery (eg, dental extraction of <3 non-molar teeth). Minor surgical procedures may be performed at a local health care provider institution.

Major surgery is defined as any invasive operative procedure that requires any of the following:

- Opening into a major body cavity (eg, abdomen, thorax, skull)
- Operation on a joint
- Removal of an organ
- Dental extraction of any molar teeth or  $\geq 3$  non-molar teeth
- Operative alteration of normal anatomy
- Crossing of a mesenchymal barrier (eg, pleura, peritoneum, dura)

It is recommended that any elective non-dental major surgery be performed at a clinical study center, when possible.

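### SAP 6.3 gives minor surgery a 72-hour minimum exclusion and major surgery none beyond the operation day, so an early postoperative bleed can count in the primary ABR after the larger procedure only

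*SAP*

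**What the plan says.** SAP 6.3, under Efficacy Period and Treatment Period, introduces its list of exclusions with: "The onset period, efficacy period and treatment period also exclude the period of following intercurrent events to avoid confounding of treatment effect". Two entries concern surgery.

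- **Major surgery:** the perioperative period is excluded. "The perioperative period is defined as the day of the surgery through the final day on which supplemental hemostatic or antithrombotic treatments are administered" under the perioperative plan.
- **Minor surgery:** "Period of minor surgery is defined as the Perioperative period of surgery above or to 72 hours from the end of surgery, whichever is later".

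The analysis periods hold for both arms: "The corresponding window is applied to on-demand arm for analysis purpose". The counted events are limited: "Only bleeding episodes that are treated with BPA/factor will be included in the primary analysis of endpoints evaluating bleeding".

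The protocol bears on this in three places.

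- Section 6.6 has the same perioperative definition, also without a minimum: "The Perioperative Evaluation Period is defined as the day of the surgery through the final day on which supplemental hemostatic or antithrombotic treatments" are given.
- Section 11.2.1 lists "Dental extraction of any molar teeth" among the criteria for major surgery, while its example of a minor procedure is extraction of fewer than three non-molar teeth.
- Section 8.2.5.1 is wider than the SAP for major surgery. It drops "bleeding episode data during and after major surgery, AT administration, major trauma" from the primary analysis and does not list minor surgery.

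SAP 2.5 records that exclusion periods for major and minor surgery were added. It gives no reason for a minimum on one and not the other.

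**The concern.** SAP 6.3.1.1 justifies the exclusions on the ground that bleeds around surgery could bias the estimated effect and make the comparison hard to interpret. One would expect the larger procedure to have at least as long a window as the smaller one. As written, the minimum sits on the smaller procedure only. When perioperative treatment ends early, the rule keeps in the primary analysis the kind of bleed it was written to keep out.

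The supportive treatment-policy analysis in SAP 6.3.1.2 removes surgical bleeds by cause, not by this window. A single postoperative bleed could therefore be dropped there and counted in the primary analysis. Protocol 11.2.1 also classes any operation on a joint as major, so the annualized joint bleeding rate is exposed to the same gap.

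What is at stake is the coherence of the primary estimand, and the avoidance of case-by-case judgement in an open-label trial about which bleeds fall inside the window.

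**Working it through.** **1. The two windows side by side.** SDay 0 is the day of surgery. The bleed is treated and no other exclusion applies.

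| Perioperative treatment ends | Bleed | After major surgery | After minor surgery |
|---|---|---|---|
| SDay 0 | 48 h after end of surgery | counted | excluded |
| SDay 2 | on SDay 3, less than 72 h after end of surgery | counted | excluded |
| 72 h or more after end of surgery | within 72 h | excluded | excluded |

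The windows differ only when treatment stops before 72 hours. No other section of either document gives major surgery a minimum in the primary analysis.

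**2. The plan's own figures.** The surgery windows carry no stated figure, so the check is on the design they feed into. Inputs from SAP 5.1: mean ABR 18 (SD 14) on demand, 4 (SD 6) on fitusiran, 14 and 28 evaluable patients, two-sided 0.05, 20% dropout. From SAP 6.3: Day 29 to Day 246, which is 246 − 29 + 1 = 218 days, so t = 218/365.25 = 0.597 years.

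- Dispersion, k = (SD² − mean/t)/mean²: on demand (196 − 30.16)/324 = 0.512; fitusiran (36 − 6.70)/16 = 1.831.
- Variance of the log rate ratio: (1/(18t) + 0.512)/14 + (1/(4t) + 1.831)/28 = 0.0432 + 0.0804 = 0.1236, so the standard error is 0.3515.
- Power: Φ(ln(18/4)/0.3515 − 1.96) = Φ(2.32) = 99.0%.
- Treating the SDs as those of annual counts gives 98.5%. A patient-weighted common dispersion gives 94% to 95%. Only the larger dispersion imposed on both arms falls below the stated level, at 87% to 90%.
- Sample size: 14/0.8 = 17.5, rounded up to 18; 28/0.8 = 35, taken to 36 for 2:1; total 54.

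The stated power above 90% and N = 54 reproduce.

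**3. Effect of one counted postoperative bleed.**

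- On that patient's ABR: 365.25/218 = 1.68.
- On the fitusiran arm mean: 1.68/28 = 0.06 (evaluable) or 1.68/36 = 0.05 (randomized).
- On the rate ratio, starting from 4/18 = 0.222. Expected fitusiran bleeds are 4 × 0.597 × 28 = 66.8. One more gives (67.8/66.8) × 0.222 = 0.226, and four more give 0.236.
- In the on-demand arm, expected bleeds are 18 × 0.597 × 14 = 150.4. One more gives 0.222 × (150.4/151.4) = 0.221.

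**4. Power with such bleeds counted.** The documents do not give a number of operations, so 0 to 4 affected fitusiran-arm bleeds is an assumed range. In 1,000 simulated trials per case (negative binomial regression, log-duration offset, no stratum term), power was 98.9% throughout. The median estimated ratio went from 0.213 with none to 0.216 with one and 0.227 with four.

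**The case against.** The strongest reply is that the gap will seldom open.

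- **Surgery should be rare.** Protocol 5.2 excludes patients with planned or anticipated surgery, and section 6.6 recommends postponing non-urgent major surgery until after the trial.
- **Coverage may normally outlast 72 hours.** Protocol Table 10 records completion of hemostatic coverage at Postoperative Visit 2 (SDay 2 to 14) or Visit 3 (SDay 28), so same-day completion is not the expected pattern.
- **Other rules catch some cases.** Antithrombin treatment has its own exclusion. Renewed bleeding at a site within 72 hours of the last injection used to treat a bleed there belongs to the original episode. BPA given for a postoperative bleed might itself be read as part of the perioperative plan and so extend the window.

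The first item stands and limits the size. The second stands in part, because SDay 2 still falls before 72 hours and the table does not rule out earlier completion. The third does not supply a general minimum. The merging rule starts from an injection used to treat a bleed or from an untreated bleed, not from prophylactic cover, and the SAP does not say whether treating a postoperative bleed belongs to the plan.

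Two stronger readings are tempting. A reader might infer a bias against fitusiran, since Protocol 6.6 has fitusiran patients follow the bleed-management principles of 6.3.1. Those principles concern dose, interval and contact with the site. Nothing says that coverage lasts a shorter or longer time in either arm. The windows also apply to both arms, and a bleed counted in the on-demand arm moves the ratio in fitusiran's favour. A reader might also infer that the major window has no end if no treatment is given. The period starts on the day of surgery, so that day is its natural minimum, and Protocol 6.6 calls for a written perioperative plan in both arms unless circumstances prevent it.

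**Conclusion.** The asymmetry is in the current SAP text and touches the primary on-treatment analysis. When perioperative treatment stops before 72 hours, a treated postoperative bleed in either arm is counted after major surgery and would be excluded after minor surgery, against the stated purpose of the exclusions. This rests on one assumption that the documents do not confirm: that coverage sometimes ends that early. It is plausible for a molar extraction and less so for longer operations.

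The size is small: 1.68 ABR units for the patient concerned, 0.05 to 0.06 on the fitusiran arm mean, and a rate ratio of 0.226 in place of 0.222 for one fitusiran-arm bleed. Power is unaffected over the assumed range, and few patients should be involved. The documents support neither an imbalance between arms nor a threat to the trial's conclusion. It is a minor drafting inconsistency that is worth correcting because the correction is simple.

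**What to change.** Before database lock, replace the two surgery entries in SAP 6.3 with one analysis window for major and minor surgery: from the day of surgery to the later of the last day of perioperative hemostatic or antithrombotic treatment and 72 hours after the end of surgery. If the difference is intended, state the reason. It would help to add whether BPA given for a postoperative bleed counts as part of the perioperative plan.

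This changes only the SAP analysis window. The protocol's Perioperative Evaluation Period and clinical care stay as they are.

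The cost is one sentence and at most about 3 days of exposure per affected operation, 3/218 = 1.4% of the efficacy period. For a patient with no bleed in those days, the shorter denominator raises the observed ABR by a factor of at most 218/215 = 1.014.
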